## 10.0 Procedures Involved

The following table outlines each of the study visits and tells what procedures will be done at each visit:

Procedure	Length of Time Required for Participants
VISIT 1A: Initial Evaluation	
Informed consent & HIPAA	30 minutes
General History and medications	3 minutes
Visual Acuity	2 minutes
Tolerability Survey & OSDI	10 minutes
Slit-lamp Examination with assessment of PROSE devices	5 minutes
R-scan (pre and post PROSE removal)	10 minutes
Slit-lamp examination (after lens removal)	5 minutes
Instructions and dispensing product	10 minutes
TOTAL TIME	75 minutes

Procedure	Length of Time Required for Participants
VISIT 1B: Evaluation after 2 weeks with buffered saline	
General History and medications	3 minutes

Visual Acuity	2 minutes
Tolerability Survey & OSDI	10 minutes
Slit-lamp examination (after lens removal)	5 minutes
R-scan (pre and post PROSE removal)	10 minutes
Instructions and dispensing product	10 minutes
TOTAL TIME	40 minutes

Procedure	Length of Time Required for Participants
VISIT 2: Week 1 after dispense Restasis	
General History and medications	3 minutes
Visual Acuity	2 minutes
Tolerability Survey & OSDI	10 minutes
R-scan (pre and post PROSE removal)	10 minutes
Slit-lamp Examination (after lens removal)	10 minutes
TOTAL TIME	35 minutes

Procedure	Length of Time Required for Participants
VISIT 3: Week 4 after dispense Restasis	
General History and medications	3 minutes
Visual Acuity	2 minutes
Tolerability Survey & OSDI	10 minutes
R-scan (pre and post PROSE removal)	10 minutes
Slit-lamp Examination (after lens removal)	10 minutes
TOTAL TIME	35 minutes

Figure 1. Table including organization of examinations done at each study visit

Test	Description
General History and Medications	Participants will be asked questions about their general, ocular and medication use histories along with contact lens use history if applicable.
Lens Evaluation	The PROSE device fit and vision will be evaluated.
Visual Acuity	The participant's vision in each eye while wearing lenses will be measured with a high contrast visual acuity chart. The participant will be asked to cover one eye and read the chart, and this procedure will be repeated for the other eye.
Slit-lamp Examination	The participant's front portion of each eye and contact lenses will be examined with a lighted microscope. The participant will be asked to place his/her chin on the chinrest and place his/her forehead against the bar and look straight ahead. The instrument's light will be shined onto the eye to visualize the ocular surface for approximately 2-3 minutes per eye.
Sodium Fluorescein/Lissamine Green	Sodium fluorescein/Lissamine Green staining will be used to evaluate ocular surface damage indicated by cell damage or death and for assessing an open vs closed PROSE device system. Corneal and conjunctival staining will be scored using the NEI Grading System.
R-Scan	Non-invasive imaging modality with automated classification of ocular redness level. Instrument used: OCULUS Keratograph 5M. The participant will be asked to place his/her chin on the chinrest and place his/her forehead against the bar and look straight ahead. The investigator will perform a scan of the eye to obtain an image of the front surface of the eye. The computer will then use an embedded software algorithm to quantify the level of redness on a scale from 0 to 4 in 0.1 increments.
Questionnaires	Subjects will be asked to fill out the following questionnaires: 
 
• Ocular Surface Disease Index (OSDI)
 
• Restasis Tolerability Questionnaire
 

*Figure 2. Table including descriptions of tests*

Statistical Analysis:

Subject data will be compared to their baseline status prior to initiating usage of the study drug. Subjects will be reevaluated at 1 week and 1 month visits and the data will be evaluated and compared to baseline. This is a small preliminary pilot study to evaluate tolerability of this treatment model utilizing Restasis. Given the small number of subjects and given our question of initial tolerability, the predominant nature of the results are observational and meant to provide an early means of addressing the question of tolerability.

The following data will be collected. They are all minimal to no risk.

- Visual acuity
  - Visual acuity will be measured on a Snellen chart and converted to logMAR values
- Tolerability survey
  - The Tolerability Questionnaire involves the subject answer a series of questions to assess their symptoms.
- Ocular Surface Disease Index (OSDI)
  - The Ocular Surface Disease Index is a validated questionnaire consisting of a group of 12 questions designed to assess symptoms of ocular surface disease. The questionnaire is administered by a trained medical staff member. All questions are answered on a scale of 0 to 4 (or the subject has an option to not answer a question). The end score is then mathematically converted to a 0-100 scale, with 0 being no symptoms and 100 being the most severe symptom score.
- Corneal staining (NEI Grading System)
  - Corneal staining is a routine ophthalmic and optometric test which utilizes Sodium Fluorescein stain on the eye to evaluate the health of the ocular surface. The amount of stain adherent to the ocular surface is then recorded utilizing standardized scales. It is minimal risk, including risk of irritation, redness, burning and stinging.
  - The NEI Grading System is a standardized method for quantifying the level of ocular surface signs noted on slit lamp examination. The scale ranges, in whole numbers, from 0 to 3, in 5 distinct sections on the cornea, with 0 indicating that the particular sign is not present and 3 being the most severe version of that specific sign (ie corneal staining, conjunctival staining, conjunctival redness) being measured. The overall score for one eye's cornea (5 sections on each cornea) ranges from 0 to 15.
- Conjunctival staining (NEI Grading System)
  - Conjunctival staining is a routine ophthalmic and optometric test which utilizes Lissamine Green stain on the eye to evaluate the health of the ocular surface. The amount of stain adherent to the ocular surface is then recorded utilizing standardized scales. It is minimal risk, including risk of irritation, redness, burning and stinging.
  - The NEI Grading System is a standardized method for quantifying the level of ocular surface signs noted on slit lamp examination. The scale ranges, in whole numbers, from 0 to 3, in 6 distinct sections on the cornea, with 0 indicating that the particular sign is not present and 3 being the most severe version of that

specific sign (ie corneal staining, conjunctival staining, conjunctival redness) being measured. The overall score for one eye's conjunctiva (6 sections on each eye's conjunctiva) ranges from 0 to 18.

- Conjunctival Redness (Efron and modified Efron scale)
  - Conjunctival redness involves the visual inspection of the ocular surface by the investigator and grading of the amount of redness on a standardized scale.
  - The Efron Grading Scales for Contact Lens Complications is a standardized method for quantifying the level of ocular surface signs noted on slit lamp examination. The scale ranges, in whole numbers, from 0 to 4, with 0 indicating that the particular sign is not present and 4 being the most severe version of that specific sign (ie corneal staining, conjunctival staining, conjunctival redness) being measured.
- Oculus Keratograph 5M R-Scan value
  - This device is a non-invasive imaging modality which takes an image of the front surface of the eye and through the use of a computerized algorithm categorizes the level of redness automatically on a continuous scale that increases in increments of 0.1 starting from 0 up to 4.
  - The investigator will image the ocular surface utilizing the Oculus Keratograph 5M device. The computer will then use an embedded software algorithm to quantify the level of redness on a scale from 0 to 4 in 0.1 increments, with 0 being no redness and 4 being the most severe redness level.

Findings for all endpoints will evaluated to measure subjective and objective differences in clinical signs and symptoms.

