### **3.0 Inclusion and Exclusion Criteria**

The participant will be eligible to participate if the following criteria apply:

1. Written Informed Consent has been obtained prior to any study-related procedures taking place
2. Subject is Male or Female, 18 years of age or older prior to the initial visit
3. Is an established wearer of PROSE devices for > 6 months in both eyes

4. Has a finalized PROSE lens design in both eyes, in the opinion of the clinician
5. The PROSE design does NOT include fenestrations
6. Subject requires PROSE devices to treat symptoms and/or signs from underlying dry eye disease, GVHD, Sjogren's syndrome, limbal stem cell deficiency, keratoconjunctivitis sicca, or ocular surface disease
7. Baseline Corneal staining grade of 2 or higher in total, both eyes combined (NEI Grading System)
8. Baseline Ocular Surface Disease Index 13 or greater
9. In the opinion of the investigator, the subject can follow study instructions
10. In the opinion of the investigator, the subject can complete all study procedures and visits
11. Able to wear PROSE device continuously for at least 6 hours at a time without removal, in each eye
12. Able to wear PROSE device for at least 10 total hours a day, in each eye
13. Able to wear PROSE device in subsequent continuous sessions of 6 hours, followed by a break to re-instill Restasis in device bowl, followed by another period of continuous wear of at least 4 hours
14. Currently using buffered preservative free normal saline (Purilens) in the device bowl or willing to transition to buffered preservative free normal saline (Purilens) use in the device bowl during the study

The participant would NOT be eligible to participate if at least one of the following criteria is met:

1. Is currently participating in any other type of eye-related clinical or research study
2. Is pregnant or nursing as reported by the subject.
3. Has a condition or is in a situation which, in the investigator's opinion, may put the subject at significant risk, may confound study outcomes, or may significantly interfere with the subject's participation in the study.
4. Has had previous ocular surgery within the past 12 weeks.
5. Currently uses or has a prior history of using Restasis in the last 3 months
6. Currently uses or has a prior history of using Cequa in the last 3 months
7. Is currently using Xiidra and has been using Xiidra for less than 3 months

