#### **5.0 Number of Subjects**

This study will enroll a minimum of 10 subjects. We expect an approximate 10% drop-out rate, so we will expect to recruit approximately 12 subjects; and the first 10 to be eligible and complete the study will be used for data analysis. All subjects will receive the study drug, Restasis (cyclosporine ophthalmic solution 0.05%).

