#### **7.0 Multi-Site Research Communication – N/A**

#### **8.0 Study Timelines**

The total duration of the subjects' participation in the study will be between 4-6 weeks. It is anticipated that to enroll all study subjects, it will take approximately 8 months. The estimated date for completion of this study is 12 months after the start of recruitment.

The study will enroll 2 groups of subjects:

- Group A: Those subjects already using preservative free buffered normal saline (Purilens) at the time of enrollment to the study

- Group B: Those subjects NOT currently using preservative free buffered normal saline (Purilens) at the time of enrollment but who are willing to be switched to preservative free buffered normal saline (Purilens) as part of the study protocol

Visit 1A:

- a. Completion of informed consent
- b. Collect past medical history, past ocular history, allergies, medications as well as habitual contact lens information, including lens design, power, and diameter.
- c. Subject's evaluation of symptoms via a baseline tolerability questionnaire and baseline Ocular Surface Disease Index (OSDI)
- d. Visual acuity assessments of both eyes (logMAR)
- e. Baseline assessment of PROSE device:
  - a. Confirm acceptable fit
- f. Baseline Oculus Keratograph 5M R-Scan with lens (automatic classification of redness)
- g. Remove lens
- h. Baseline Oculus Keratograph 5M R-Scan without lens (automatic classification of redness)
- i. Baseline slit lamp examination (without lens) including:
  - a. anterior segment and ocular surface
  - b. conjunctival redness (Efron Grading Scale, Modified Efron Grading Scale)
  - c. corneal staining with sodium fluorescein (NEI Grading System)
  - d. conjunctival staining with lissamine green (NEI Grading System)
- j. Initiation of study, with either:
  - a. Group A (subjects currently using Purilens): Dispense Restasis for initiation of usage in device bowl
    - i. Instructions for use: 1 drop of RESTASIS in the lens bowl followed by filling the remainder of the lens bowl with Purilens qAM. After 6 consecutive hours of wear, remove and reapply lens with 1 drop of RESTASIS in the lens bowl followed by filling the remainder of the lens bowl with Purilens. Wear lens without removal for at least 4 more consecutive hours.
  - b. Group B (subjects NOT currently using Purilens): the subject will be provided Purilens for use over the next two weeks and return for Visit 1B
- k. Reapply lens and wait 15 minutes

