## 9.0 Study Endpoints

The study endpoints to analyze safety, tolerability and efficacy are as follows:

- a) Visual Acuity (logMAR)
- b) Tolerability questionnaire
- c) Ocular Surface Disease Index (OSDI)
- d) Corneal staining with sodium fluorescein (NEI Grading System)
- e) Conjunctival staining with lissamine green (NEI Grading System)
- f) Conjunctival redness, Efron and modified Efron scale
- g) Oculus Keratograph 5M R-Scan value

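### The logMAR acuity endpoint is a converted Snellen reading with unstated lines and scoring, so its steps may be uneven and it loses some precision (minor)

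*Protocol*

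**What the plan says.** Protocol Section 9.0 opens its list with "The study endpoints to analyze safety, tolerability and efficacy are as follows" and puts acuity first of seven items, in logMAR. Each visit list in Section 8.0 repeats the unit: "Visual acuity assessments of both eyes (logMAR".

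Section 10.0 describes the measurement twice. The table of tests says "The participant's vision in each eye while wearing lenses will be measured with a high contrast visual acuity chart". The Statistical Analysis text later in the section names the chart: "Visual acuity will be measured on a Snellen chart and converted to logMAR values".

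Neither document gives the chart's lines, whether a partly read line earns credit, or the conversion rule. The protocol has no acuity criterion for entry, no expected baseline acuity and no threshold for lines lost. The SAP does not mention acuity by name. It plans a paired t-test for before/after data, with significance at P ≤ 0.05.

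On sample size, Section 5.0 says that "the first 10 to be eligible and complete the study will be used for data analysis".

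**The concern.** A paired t-test uses the size of each subject's change, so it matters how finely that change is recorded. A Snellen line written as a logMAR number is still a Snellen line. On many Snellen charts the lines are unevenly spaced in logMAR, so one line can mean 0.08 in one subject and 0.30 in another.

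The study's stated goal is tolerability and safety (Section 1.0). Sections 12.0 and 13.0 list visual disturbance, mostly blurring, among the reported reactions to the drug. Acuity is the only listed endpoint that measures vision by examination. With 10 subjects analysed, a few coarse steps can noticeably widen the spread of the changes.

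Entry does not exclude eyes with poor vision: "Subject requires PROSE devices to treat symptoms and/or signs from underlying dry eye disease, GVHD, Sjogren's syndrome, limbal stem cell deficiency" is among the qualifying conditions, and no acuity limit is set.

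**Working it through.** The plan states no figure for acuity resolution, SD or power, so there is none to reproduce.

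**Inputs from the documents**
- Analysed sample: 10 (Protocol Section 5.0).
- Paired t-test at 0.05 (SAP). The number of sides is not stated; two-sided is assumed.

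**Assumed inputs**
- Traditional chart: 20/400, 200, 100, 70, 50, 40, 30, 25, 20, 15.
- Whole-line scoring.
- True loss 0.10 logMAR, SD of true change 0.10, test noise SD 0.05.

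**Step 1: size of each step.** Step = log10(larger denominator / smaller denominator).

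| Adjacent lines | Step (logMAR) |
|---|---|
| 20/400 to 20/200 | log10(2) = 0.301 |
| 20/200 to 20/100 | log10(2) = 0.301 |
| 20/100 to 20/70 | 0.155 |
| 20/70 to 20/50 | 0.146 |
| 20/50 to 20/40 | 0.097 |
| 20/40 to 20/30 | 0.125 |
| 20/30 to 20/25 | 0.079 |
| 20/25 to 20/20 | 0.097 |
| 20/20 to 20/15 | 0.125 |

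The largest step depends on the chart. It is 0.301 if 20/200 and 20/100 are adjacent, 0.176 if lines such as 20/300 and 20/150 are present, and 0.107 on log-spaced lines.

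**Step 2: chance that a 0.10 loss leaves the recorded line unchanged.** With true acuity uniform within a gap, this is max(0, 1 − 0.10/step).
- Step 0.301: 1 − 0.332 = 0.67.
- Steps 0.146 and 0.155: 0.32 and 0.35.
- At 20/50 or better: 0 to 0.20.
- Log-spaced lines: 0 to 0.07.

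**Step 3: effect on mean and spread in a 0.301 gap.** A loss is recorded as 0.301 with probability 0.332, otherwise as 0.
- Expected recorded change = 0.332 × 0.301 = 0.10, so the mean is preserved.
- SD from rounding alone = 0.301 × √(0.332 × 0.668) = 0.142, even if every subject loses exactly 0.10.

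**Step 4: power of the paired t-test.** Simulation with n = 10, one reading per subject and baselines uniform in the stated range. Letter scoring uses steps of 0.02.

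| Baseline range | Letter scoring | Whole Snellen lines |
|---|---|---|
| 20/20 to 20/40 | 63% | 59% |
| 20/40 to 20/200 | 63% | 46% |
| 20/100 to 20/200 | 63% | 36% |

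In the middle row the SD of recorded change rises from about 0.12 to about 0.17.

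If two eyes are averaged per subject, taking the same true change in both, the middle row becomes about 71% against 61%.

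**The case against.** The strongest reply is that this is a disclosed and ordinary method in a pilot whose results Section 10.0 calls predominantly observational. Several parts of that reply stand.

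- **No contradiction.** A reader might infer that a logMAR endpoint conflicts with a Snellen chart. It does not, because the protocol states the conversion openly.
- **No hidden one-line loss.** A reader might infer that the method conceals a one-line loss in a safety endpoint. A full line lost on the chart in use always changes the reading. What can be missed is a 0.10 logMAR loss, which is a line on a different chart. The plan has no lines-lost rule for the chart to defeat, and acuity serves safety, tolerability and efficacy jointly.
- **The 0.30 step is not in the documents.** It follows from an assumed chart and whole-line scoring. Crediting letters on partial lines would shrink the problem.
- **Poor vision is not shown.** Acuity is tested with the device on, and Section 2.0 says a rigid lens masks surface irregularities. Section 3.0 requires more than 6 months of wear and a finalized design in both eyes. Some eyes may still see poorly, but no baseline figure says how many.
- **One eye moves the mean only a little.** A single 0.30 step shifts a mean of 10 by 0.30/10 = 0.03, or by 0.30/20 = 0.015 if 20 eyes are averaged.
- **Vision is watched in other ways.** Adverse events are recorded, and subjects are told to call with new visual symptoms (Section 13.0).

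The observational label does not dispose of the point. Section 23.0 and the SAP still plan hypothesis tests, and a descriptive reading of individual eyes would be just as coarse.

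**Conclusion.** The point holds as a minor weakness in measurement. The endpoint's resolution is set by a Snellen chart whose lines and scoring are not stated, and conversion to logMAR does not improve it.

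On the assumed traditional chart with whole-line scoring, the cost is about 4 percentage points of power (63% to 59%) at 20/20 to 20/40. It is about 17 points (63% to 46%) if baselines span 20/40 to 20/200, and about 10 points (71% to 61%) in that range if two eyes are averaged. These figures also rest on the assumed SDs. The documents do not say how eyes are combined or what baseline acuity to expect, so the actual loss cannot be placed within this range. On log-spaced lines it would be smaller.

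The harm is to precision and to the reading of individual eyes worse than 20/100. The documents do not support a claim of a biased mean or of a safety signal that the chart is bound to miss.

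**What to change.** In the Statistical Analysis text of Protocol Section 10.0, replace the sentence on Snellen measurement with:

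> Acuity will be measured in each eye, with lenses on, on a high-contrast logMAR chart scored letter by letter (0.02 logMAR per letter), using the same chart, distance and lighting at all visits.

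This also settles the chart, the scoring and the conversion, and agrees with the test description earlier in the section.

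The cost is one sentence, a standard logMAR chart and about one extra minute per eye (an estimate). The visit tables in Section 10.0 allow 2 minutes for acuity, so that entry would become about 4 minutes. The totals of 75, 40, 35 and 35 minutes would become about 77, 42, 37 and 37.

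If a Snellen chart is kept, state its lines and the conversion rule, record the letters read on partial lines and credit them in the conversion. Keep all subjects in the mean; with 10 analysed, leaving any out would cost more precision than the coarse steps justify.

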**[contact]**

**[[contact]](mailto:[contact])**

## **1.0 Objectives**

The goal of this prospective observational pilot study is to evaluate the tolerability and safety of RESTASIS (cyclosporine ophthalmic solution 0.05%) when added to the PROSE (Prosthetic Replacement of the Ocular Surface Ecosystem) lens reservoir in patients with ocular surface disease (OSD). Secondary endpoints include early (1-month) efficacy data for ocular signs and symptoms.

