### **RESTASIS (cyclosporine ophthalmic solution 0.05%) (AbbVie Inc.)**

RESTASIS (cyclosporine ophthalmic solution 0.05%) is a topical immunomodulator indicated to increase tear production in patients with ocular surface inflammation associated with keratoconjunctivitis sicca. RESTASIS appears as a translucent homogenous emulsion. The osmolarity is 230 to 320 mOsmol/kg and the pH of the solution is 6.5-8.0. RESTASIS is a FDA approved drug for the increase of tear production in patients with keratoconjunctivitis sicca (dry eye syndrome). FDA approval initially occurred in 1983 and was most recently approved as of October 2003.

The ingredients for RESTASIS are listed below:

- Active Ingredients: Cyclosporine 0.05%
- Inactive Ingredients: Glycerin, castor oil, polysorbate 80, carbomer copolymer type A, purified water, and sodium hydroxide to adjust pH.

"In clinical trials the most common adverse reaction following the use of RESTASIS® was ocular burning (17%). Other reactions reported in 1% to 5% of patients included conjunctival hyperemia, discharge, epiphora, eye pain, foreign body sensation, pruritus, stinging, and visual disturbance (most often blurring)".

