**Novel Use of Cyclosporine Ophthalmic Emulsion 0.05% in a PROSE Device**

**NCT#: NCT04918823**

**Version: 8/27/2024**

## Statistical Analysis

Statistical analysis was performed using Visual Studio Code (Microsoft Corp., Redmond WA) with python version 3.9.12. Subject data post-treatment was compared to their baseline data, collected prior to initiating use of the study drug. For Group A, the data collected at Visit 1A was considered to be their baseline data pre-intervention. For Group B, the data collected at Visit 1B was considered to be their baseline data (post-initiation of Purilens and pre-initiation of cyclosporine). The core algorithm used was based on statistical functions module `scipy.stats`. For univariate data analysis (before/after visits), paired t-test was performed since every patient received treatment. Paired t-test was conducted by `scipy.stats.ttest_rel` and <https://www.statskingdom.com/paired-t-test-calculator.html>. For bi-variate data, two-way ANOVA (Analysis of variance) was performed. Two-way ANOVA was conducted by `sm.stats.anova_lm(model)` function. The significance level was set to a P-value of  $\leq 0.05$  in all instances of analysis.

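### Tolerability is the study's goal, but the analysis drops subjects who stop and specifies only a change-from-baseline test in 10 completers, which cannot show that the regimen was tolerated

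*Protocol*

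**What the plan says.** Section 1.0 of the Protocol states the aim: "The goal of this prospective observational pilot study is to evaluate the tolerability and safety of RESTASIS" in the lens reservoir. One-month efficacy is secondary.

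Section 9.0 puts seven measures in a single unranked list, introduced by "The study endpoints to analyze safety, tolerability and efficacy are as follows". The tolerability questionnaire is one of them. Section 10.0 says of it: "The Tolerability Questionnaire involves the subject answer a series of questions to assess their symptoms". The OSDI, NEI staining, Efron and R-Scan measures each get a numerical range in that section; the questionnaire does not.

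The analysis is described in three places:

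- Protocol Section 10.0, Statistical Analysis: comparison with baseline at 1 week and 1 month, with results described as mainly observational because the study is small.
- Protocol Section 23.0: a menu of hypothesis tests for differences from baseline (t-tests, signed-rank tests, ANOVA, general linear models, correlation, regression).
- SAP: "For univariate data analysis (before/after visits), paired t-test was performed since every patient received treatment". Two-way ANOVA is named for data called bi-variate, and P ≤ 0.05 applies throughout.

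On who is analysed, Section 5.0 says that "the first 10 to be eligible and complete the study will be used for data analysis". Section 15.0 withdraws subjects who cannot complete the protocol tasks, or whom the investigator takes off for an adverse event, and excludes the data of withdrawn subjects. Section 13.0 requires every adverse event to be recorded with the action taken, including discontinuation, but no summary of these records is specified.

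**The concern.** Stopping is the plainest sign that a regimen is not tolerated. Here stopping is also what removes a subject from the analysis. The protocol tasks include the two wear periods with drug in the reservoir, so a subject who cannot manage them is withdrawn under Section 15.0 and then excluded. Among the subjects analysed, completion is 100% by construction.

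For those who remain, the plan offers a test of no mean change. Failing to reject that hypothesis in 10 subjects says little about whether symptoms worsened, and a mean can conceal one or two subjects who did badly. No count, proportion or confidence interval is specified to set beside the P value. A plan followed as written could therefore give a favourable answer to its main question whether or not the regimen was tolerated.

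**Working it through.** **1. The plan's own figure.** Section 5.0 says: "We expect an approximate 10% drop-out rate, so we will expect to recruit approximately 12 subjects". To have 10 completers with 10% drop-out, 10 / (1 − 0.10) = 11.1, rounded up to 12. The figure reproduces. It is a recruitment allowance; no power or effect size supports the 10.

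**2. Effect of analysing completers only.** Suppose, for illustration, that 12 subjects are dosed and 2 stop for intolerance.

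| Set | Stopped for intolerance | Exact 95% CI |
|---|---|---|
| All dosed | 2/12 = 16.7% | 2.1% to 48.4% |
| As planned (10 completers) | 0/10 = 0% | 0% to 30.8% |

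The planned set returns 0/10 however many subjects stop, provided 10 others complete.

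**3. Power of the paired t-test.** Inputs: n = 10 (Section 5.0) and α = 0.05 (SAP). Sidedness is not stated, so both forms are shown. The documents give no SD or effect size, so the worsening d, in SDs of the paired differences, is an assumption shown over a range. Power comes from the noncentral t distribution with 9 df and noncentrality d√10. At d = 0.5 the noncentrality is 0.5 × 3.162 = 1.58, against a two-sided critical value of 2.262.

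| d | Two-sided | One-sided |
|---|---|---|
| 0.3 | 13.6% | 22.2% |
| 0.5 | 29.3% | 42.7% |
| 0.8 | 61.6% | 75.4% |
| 1.0 | 80.3% | 89.8% |

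Two-sided power reaches 50% at d of about 0.69 and 80% at about 1.0. At d = 0.5, a signed-rank test gives about 28% (simulated, normal changes), and analysing all 12 subjects by t-test gives 35.3%.

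**4. What a non-significant result leaves open.** The 95% CI half-width is 2.262/√10 = 0.72 SD. An observed mean worsening of 0.5 SD would have the interval 0.5 ± 0.72, or −0.22 to 1.22 SD. It would be reported as non-significant although a worsening above 1 SD is not excluded.

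**5. A mean hides individuals.** Let 2 of 10 worsen by the same amount c and 8 not change.

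- Mean = 0.2c.
- SD = c√[(2 × 0.8² + 8 × 0.2²)/9] = c√(1.60/9) = 0.4216c.
- Standard error = 0.4216c/√10 = 0.1333c.
- t = 0.2/0.1333 = 1.5 on 9 df; two-sided P = 0.17.

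The amount c cancels, so P is 0.17 however severe the worsening. With 1 of 10 worsening, t = 1.0 and P = 0.34.

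**6. The alternative summary.** Exact (Clopper-Pearson) two-sided 95% lower limits for the proportion tolerating: 10/10 gives 0.025^(1/10) = 69.2%; 9/10 gives 55.5%.

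**The case against.** The strongest reply is that this is a small pilot and says so. Section 10.0 calls the results mainly observational and an early look at tolerability, so low power is expected and is not an error in itself. That stands. But an observational aim calls for description and estimation, and neither document specifies a descriptive tolerability summary.

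Three stronger readings are tempting, and the documents do not support them:

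- **That the SAP assigns the t-test to tolerability.** It never mentions tolerability or the questionnaire. It gives the t-test for before/after data in general, also names two-way ANOVA, and Section 23.0 lists further methods. What can be said is that comparison with baseline is the only kind of analysis stated.
- **That the plan treats P > 0.05 as tolerated.** No text says so. The plan merely does nothing to prevent that reading.
- **That a worsening would be missed whatever its size.** At 1.0 SD two-sided power is about 80%. Failure to reject is the likelier outcome only below about 0.69 SD.

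It is also fair to say that individual intolerance is not lost from the record, since Section 13.0 captures adverse events and discontinuations. What is missing is a rule that carries them into the results. Finally, the questionnaire's items are not in the documents, so no criticism of its content or scale is made here, and it cannot be assumed to ask about burning or stinging.

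**Conclusion.** The point holds in this form and should be acted on. The completers-only rule and the exclusion of withdrawn subjects bias the answer to the study's main question towards good tolerability; in the illustration, 2/12 becomes 0/10. This needs no assumption about the questionnaire, only that some subjects stop for intolerance. Separately, a non-significant mean change in 10 subjects is not evidence of tolerability. A worsening of 0.5 SD would be missed in about 71% of such studies two-sided and 57% one-sided. Those figures rest on an assumed effect in SDs of the paired differences and on approximately normal changes. At that effect size the conclusion does not depend on sidedness, on t-test or signed-rank, or on 10 or 12 subjects. The stated observational intent tempers the seriousness but does not fill the gap.

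**What to change.** In the SAP:

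- Make the main tolerability summary the number and proportion of all subjects who received at least one dose of Restasis and continued to week 4 without stopping for an ocular reason, with an exact (Clopper-Pearson) 95% CI. Group B subjects who leave before Visit 1B are not dosed and fall outside the denominator.
- Report the number of dosed subjects with new or worse ocular burning or stinging, with exact 95% CI, from the adverse-event records in Section 13.0, and from the questionnaire if it has such an item.
- Report questionnaire change as an estimate with 95% CI, and state that P > 0.05 will not be read as evidence of tolerability.

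In the Protocol, amend Sections 5.0 and 15.0 so that withdrawn subjects count in this summary and in a summary of adverse events. If the analysis has already been done, as the SAP's past tense suggests, label the new summary post hoc.

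The cost is a short SAP paragraph and two protocol edits, with no new visits or subjects. The summary needs the reason for stopping for every withdrawn subject. Section 13.0 captures discontinuation as an action taken for an adverse event; other withdrawals may need a check of source records. The downside is that the wide intervals will show how little so few subjects can exclude.
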